1. BACKGROUND AND STUDY RATIONALE

Medications have significant potential in the treatment of acquired hearing loss, but much remains unknown about how these drugs behave in the inner ear. In earlier work we demonstrated human perilymph sampling for locally delivered methylprednisolone (Bird et al. 2007). Our animal modelling builds on earlier work by others (Ford et al. 1997) and has identified adenosine receptors as another possible vector for cochlear protection (Vlajkovic et al. 2010, 2014; Chang et al. 2017). Adenosine is an endogenous neuromodulator and a cytoprotective substance released from tissues in response to stress (Fredholm 2007). This occurs through its action on four G protein-coupled receptors designated A1, A2a, A2b and A3 (Vlajkovic et al. 2009). Two ligands binding to the adenosine A2 receptor (A2AR) have demonstrated otoprotective effects.

Istradefylline, a A2AR antagonist, is used in Parkinson's disease and we have shown this reduces deafferentation of inner hair cells and improves the survival of afferent synapses after excitotoxic injury (Han B et al 2019). Cochlear injury which is mostly due to oxidative stress or glutamate excitotoxicity, such as with the chemotherapy agent cisplatin or noise induced injury, can be reduced by blocking the A2AR which then tips the balance of adenosine towards the A1R environment which is strongly otoprotective. It is theorised this could have benefit in cisplatin induced hearing loss and high frequency hearing loss associated with stapedectomy and other surgical procedures (Babbage et al 2017).

Regadenoson is A2AR agonist, commonly used as a cardiac stimulant in myocardial perfusion tests. Our group have also demonstrated that it suppresses cochlear inflammation in an animal model (Tan 2015). It is thought that it may have a role in preserving residual hearing during cochlear implantation.

Systemic side effects from these agents will be minimised if they are delivered via an intratympanic route (Liu et al. 2013). It is anticipated that the plasma concentrations of drug delivered transtympanically will be an order of magnitude less than the established safe serum levels for the established systemic uses of these drugs in Parkinson's disease and myocardial perfusion tests. Additionally, we will be administering these A2AR ligands while the patient is under general anaesthetic and will be having their cardiovascular system closely monitored by an anaesthetist.

Drugs delivered intratympanically must stay in contact with the round window membrane and annular ligament of the oval window for a long enough period to enable sufficient diffusion into the cochlea. Poloxamer 407 is a thermoreversible gel in which drugs may be suspended (Giuliano et al. 2018) and slowly released into the middle ear in the region of the round window membrane. The slow release should enable a more constant diffusion process across the membrane and more reliable concentrations within the cochlear fluids than would injection of a solution (Musazzi et al. 2018).

We aim to study the pharmacokinetic properties of both of these agents when delivered via a slow release intratympanic method. First, via in-vitro experiments to measure the drug elution over time from the gel. Then in patients undergoing surgery with routine exposure of the inner ear (translabyrinthine tumour removal or cochlear implantation) we will measure both the plasma and perilymph drug concentration at different time points to establish the safety of a transtympanic injection of these agents and help identify therapeutic concentrations of the drugs. These translational studies are critical to establish a safe and effective delivery system in preparation for clinical trials of efficacy.

1.1 Therapeutic agents

1.1.1 Istradefylline - The precise mechanism of action is unknown. Studies have demonstrated it to be an adenosine A2a receptor antagonist. It is used in Parkinson's disease as adjunctive treatment to levodopa/cardidopa and recommended dosing is 20-40mg daily orally. Istradefylline is completely metabolised primarily by CYP1A1 and

CYP3A4. The mean terminal half life is approximately 83 hours. Systemic side effects include dizziness, anorexia, insomnia, and constipation.

1.1.2 Regadenoson - Regadenoson is an adenosine derivative and selective A_{2a} receptor agonist. Regadenoson rapidly increases coronary blood flow by inducing coronary vasodilation. It is used as a pharmacological stress agent for radionuclide myocardial perfusion imaging. It is renally excreted and the metabolism is unknown. Recommended dosing is 0.4mg (within 5ml saline) intravenously. The mean terminal half life is 2 hours. Due to its cardiac effects the systemic side effects include dyspnoea, headache, flushing, angina and nausea.

2. STUDY OBJECTIVES

Building on the background of our established human perilymph sampling methodology for transtympanically delivered methylprednisolone, we aim to extend this technique to adenosine A_{2a} receptor ligands bound to a slow release gel. Specifically, we seek to perform both in-vitro and in-vivo trials to establish the safety and therapeutic concentrations of intratympanic Istradefylline and Regadenoson. These two studies will then provide the foundation for future clinical trials with these ligands to investigate the therapeutic benefit in humans on hearing and balance preservation.

3. STUDY DESIGN

3.1. OVERVIEW OF STUDY DESIGN

The design of the first part of the study establishes the properties of drug release from the poloxamer gel for both Istradefylline and Regadenoson. While both agents have been polymerised to Poloxamer 407 in animal studies, there is no data on what the actual concentration of liberated drug is over time. This is important in humans because too low a concentration will be sub-therapeutic and too high a concentration risks stimulating other adenosine receptors which may alter the desired therapeutic effect.

The therapeutic agents will be sourced from their manufacturers: Istradefylline (Sigma), Poloxamer-407 gel (Sigma) and Regadenoson (Sapphire Bioscience). Based on prior animal studies, the gels will be prepared at 17% w/w in cold distilled water. Istradefylline 1 mM stock solution will be prepared in 40-50% Dimethyl Sulfoxide (DMSO) and then diluted down to 200 nM. Regadenoson will be similarly prepared with 2.5 mg of drug dissolved in 2 ml DMSO before being diluted to 1:100 to give a 1% DMSO concentration. The drug solutions will then be mixed with the 17% w/w poloxamer and placed on ice until fully dissolved. To model liberation of the drug from the gel in the approximately 1 mL volume of the human middle ear, 1 mL of thermoreversible gel will be warmed to body temperature (37 degrees Celsius). To approximate the fluid volume of the cochlea, 100 microlitres of saline will be placed on the gel and 20 microlitre aliquots taken at 30 minutes, 2 hours, 4 hours and 1 week and analysed by liquid chromatography - tandem mass spectrometry to establish the liberation of the drugs from the gel.

The design of the second part of the study involves adults who will already be having their inner ear exposed with translabyrinthine vestibular schwannoma removal (N= approximately 15), or cochlear implantation (N=approximately 20). We will establish the systemic safety by first performing this on patients undergoing translabyrinthine procedures

which are inherently longer and more closely monitored by the anaesthetist. We will then perform interim analysis after 6 translabyrinthine procedures for each drug. When we have demonstrated safe (low) systemic levels, we can then extend to include CI patients.

Following induction of anaesthesia, the drug-poloxamer gel will be injected transtympanically and applied over the round window membrane and the standard operation will proceed. Plasma samples will be taken at 30 minutes, 2 and 4 hours after placement of the gel. At the time of labyrinthectomy or electrode insertion, time since drug-gel injection will be noted and 20 microlitres of perilymph will be sampled from the round window using a Hamilton syringe. The perilymph will then sent for analysis using the liquid chromatography - tandem mass spectrometry detection method to ascertain the drug concentration within the perilymph of the cochlea basal turn, confirming delivery of drug. During the anaesthetic the anaesthetist monitors the patient for any signs of cardiac stress. For this study we aim to recruit 20 patients (N=10 each of Istradefylline and Regadenoson).

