3.2. STUDY ENDPOINTS

1. In vitro study: The rate of diffusion from the poloxamer gel into saline will be measured at separate time intervals in order to determine the liberation of drug from the poloxamer gel.
2. In vivo study:
 1. Establish the safety of the adenosine ligands topically in the middle ear. This will be through serial measurement of plasma concentrations and systemic (cardiovascular) effects
 2. Establish a middle ear delivery system of the adenosine ligands which is consistent

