4.2. ESTABLISHING RATE OF LIBERATION OF THE DRUG FROM GEL

4.2.1. One (1)ml of the warmed drug will be placed in an Eppendorf tube. 100 micro litres of saline will be placed on it and the Eppendorf tube placed in a 37 degree water bath. At 30 minutes, 2 hours, 4 hours and 1 week 20 microlitres of saline will be removed by micropipette and sent for analysis using the liquid chromatography - tandem mass spectrometry detection method. After each 20 micro litre aliquot is removed it will be replaced by the same amount of saline to ensure the same concentrations.

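### With saline one tenth of the gel volume, a 1-week plateau in the in-vitro test cannot be told apart from a filled receiver, so it cannot give the extent or duration of release

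*Protocol*

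**What the plan says.** Protocol sections 3.1 and 4.2 describe the same bench test. For the donor, "1 mL of thermoreversible gel will be warmed to body temperature". For the receiver, "To approximate the fluid volume of the cochlea, 100 microlitres of saline will be placed on the gel". Section 4.2 gives the sampling: "At 30 minutes, 2 hours, 4 hours and 1 week 20 microlitres of saline will be removed". It adds: "After each 20 micro litre aliquot is removed it will be replaced by the same amount of saline to ensure the same concentrations".

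The in-vitro endpoint in section 3.2 is a rate: "The rate of diffusion from the poloxamer gel into saline will be measured at separate time intervals", with the aim of determining how the drug is liberated from the gel. Section 3.1 introduces this part of the study as establishing the release properties of the gel for both drugs, and gives the reason that "there is no data on what the actual concentration of liberated drug is over time". The background in section 1 rests the choice of gel on prolonged release: "The slow release should enable a more constant diffusion process across the membrane".

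The protocol gives no gel-to-saline partition ratio, no diffusivity and no correction for the exchanged saline. It plans no sample between 4 hours and 1 week.

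**The concern.** A release test can follow the gel only while the receiver has room for more drug. Here the receiver is 0.1 mL against 1 mL of gel, and only a fifth of it is renewed at each sample. Once the saline is in balance with the gel, net transfer stops, whatever is left in the gel. From then on the reading is set by the volume ratio and the partition ratio, not by how the gel releases drug.

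This matters most at 1 week, the only sample later than 4 hours and so the only one that bears on prolonged release. If that reading is at the plateau, it could be reported as sustained release, or as release that is complete, when it shows neither. Correcting for the dilution at each exchange recovers the drug that was removed. It does not recover release that the small receiver prevented.

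**Working it through.** **Inputs from the protocol (sections 3.1 and 4.2).** Gel volume 1 mL; saline volume 0.1 mL; sample 0.02 mL, replaced each time; samples at 30 minutes, 2 hours, 4 hours and 1 week. The protocol states no released fraction, so there is no figure of its own to reproduce.

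**Assumption.** K is the ratio of drug concentration in saline to that in gel at equilibrium. The documents do not give it. I take K = 1 as the base case and show 0.5 and 2. Concentrations are relative to the starting gel strength.

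**Step 1: first equilibrium.** Share of the load in the saline = 0.1K / (1 + 0.1K). At K = 1 this is 0.1 / 1.1 = 9.1%, and the saline reads 1 / 1.1 = 0.909.

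**Step 2: upper limit with the planned exchanges.** Assume full equilibration before every sample. At K = 1 each reading is the remaining load divided by 1.1, and each exchange removes 0.02 times the reading.

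- Sample 1: 1 / 1.1 = 0.909; load left 1 − 0.0182 = 0.9818
- Sample 2: 0.9818 / 1.1 = 0.893; load left 0.9640
- Sample 3: 0.9640 / 1.1 = 0.876; load left 0.9464
- Sample 4 (1 week): 0.9464 / 1.1 = 0.860

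Drug removed in the first three samples is 1 − 0.9464 = 0.0536. Drug in the saline at the end is 0.1 × 0.860 = 0.0860. The total that has left the gel is 0.1396, about 14%; about 86% is still in the gel.

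**Step 3: range for K.**

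| K | Out at first equilibrium | Cumulative at 1 week |
|---|---|---|
| 0.5 | 0.05 / 1.05 = 4.8% | 7.5% |
| 1 | 9.1% | 14.0% |
| 2 | 0.2 / 1.2 = 16.7% | 24.7% |

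**Step 4: what the four samples would read.** One-dimensional diffusion from the gel into well-mixed saline, K = 1, assumed tube radius 0.45 cm, with the planned exchanges. The diffusivities D are assumed.

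| Gel | 30 min | 2 h | 4 h | 1 week |
|---|---|---|---|---|
| Instant equilibration | 0.91 | 0.89 | 0.88 | 0.86 |
| D = 4e-6 cm²/s | 0.40 | 0.56 | 0.61 | 0.88 |
| D = 1e-6 cm²/s | 0.24 | 0.37 | 0.43 | 0.86 |
| D = 1e-7 cm²/s | 0.09 | 0.15 | 0.18 | 0.66 |

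At 1 week the first three rows agree to within about 2%, so that reading alone does not separate them. At 4 hours they are clearly apart. The slowest gel is still below the ceiling at 1 week.

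The pattern does not depend on K = 1. At K = 0.5 the 1-week readings for instant equilibration, D = 1e-6 and D = 4e-6 are 0.463, 0.462 and 0.466. At K = 2 they are 1.505, 1.516 and 1.596.

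**Step 5: a larger receiver.** With 10 mL of saline on 1 mL of gel and K = 1, the capacity limit is 10 / 11 = 90.9% of the load. In the same model, cumulative release at 1 week is about 17% (D = 1e-7), 53% (D = 1e-6) and 86% (D = 4e-6), against about 91% for instant equilibration. Gels that read alike at 1 week in the planned tube now separate.

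**The case against.** The best defence is that 100 microlitres is a deliberate choice with a stated reason, to match the fluid volume of the cochlea. The gap that section 3.1 names is the concentration of freed drug over time, since too little may be sub-therapeutic and too much may act on other adenosine receptors. For that question a cochlea-sized receiver is defensible. This stands, and it is why the tube should be kept. It does not cover the other purpose in sections 3.1 and 3.2, which is to establish the release properties and rate of liberation.

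The second defence is that the endpoint rests on four samples, not one. This also stands. A reader might infer that the test cannot show slow release at all, or that no rate can be taken from it. The documents do not support that: at 4 hours instant equilibration would read 0.88 against 0.43 to 0.61 for the two intermediate gels, and a rise from 4 hours to 1 week would show that release went on. Release slow enough to stay under the ceiling would also be visible at 1 week. The protocol gives no diffusivity, so that case cannot be set aside. What the series cannot do is date a late rise, because nothing is sampled between 4 hours and 1 week.

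Third, the protocol ties no dose or go/no-go decision to the 1-week value. That is correct and limits the severity.

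**Conclusion.** The concern holds in a limited form. The planned tube is limited by receiver capacity: it can show release of about 9% of the load at first equilibrium and about 14% cumulatively by 1 week, if gel and saline hold the drug equally. A reader might take 14% as a fixed bound. It is one only for a saline:gel ratio of 1 or less; the limit is about 7.5% at a ratio of 0.5 and about 25% at 2, and the documents do not give the ratio. For the same reason, a plateau concentration cannot be converted into a fraction of drug that the gel is able to release.

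The samples at 30 minutes, 2 hours and 4 hours can inform an early rate if they precede equilibrium. A 1-week plateau cannot be told apart from a filled receiver, so the extent and duration of release cannot be estimated from it. The diffusion figures also rest on an assumed tube radius, assumed diffusivities and well-mixed saline. Severity is minor to moderate.

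**What to change.** 1. Keep the 100 microlitre tube, described as a model of concentration in a cochlea-sized volume.
2. Take the early rate only from its pre-equilibrium samples, corrected for exchanged saline: drug released by sample n = 0.1 mL × current reading + 0.02 mL × sum of the earlier readings.
3. State in section 4.2 that a 1-week plateau in this tube will not be read as sustained or complete release.
4. Add to section 4.2 one parallel tube per drug with a receiver large against the gel, for example 10 mL of saline on 1 mL, at the same sampling times. Assay the starting gel and the residual gel at 1 week.
5. In section 3.2, make the cumulative percentage of the load released in that tube the measure of liberation.

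The cost is one bench tube and a few extra assays per drug; no patients are involved. The drawback is lower concentrations. At equal partitioning the 10 mL receiver reaches at most 1 / 11, about 9%, of gel strength, and less at early times or with slow release (17% released gives 0.17 / 10 = 1.7%). The assay limit for both drugs must be checked before the volume is fixed.

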5.2 DETAIL OF PROCEDURE

1. Prepared drug-poloxamer gel solution will be placed in a 1ml syringe with a 22G spinal needle attached
2. After the induction of general anaesthesia the WHO surgical safety checklist will be performed to ensure the correct procedure, site and side.
3. With an operating microscope the drug-poloxamer gel solution will be placed trans-tympanically through the antero-superior portion of the tympanic membrane over the round window.
4. The elective surgical procedure will then proceed as planned with a cortical mastoidectomy, posterior tympanotomy and exposure of the bony labyrinth.
5. Prior to the opening of the inner ear the middle ear will be washed out with 20 mL normal saline to ensure the complete removal of the drug-poloxamer gel.
6. The middle ear will be examined for anatomical variations, such as obstructing mucosal folds over the round window.
7. A micro syringe will then be used to withdraw 20 micro litres of perilymph from the round window

8. Serum for drug levels will be taken at ...
9. The rest of the procedure will then proceed as planned

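### The interim step that opens dosing to CI patients names drug levels only, although the protocol's own safety endpoint also includes cardiovascular effects

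*Protocol*

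**What the plan says.** Section 3.1 starts the in-vivo part in translabyrinthine patients, whose operations it describes as longer and more closely monitored, with the aim of establishing systemic safety there. It continues: "We will then perform interim analysis after 6 translabyrinthine procedures for each drug". The condition for moving on is "When we have demonstrated safe (low) systemic levels, we can then extend to include CI patients". No other condition for extension appears.

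Section 3.2 gives the in-vivo safety endpoint two components: "This will be through serial measurement of plasma concentrations and systemic (cardiovascular) effects".

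Section 1 expects that "plasma concentrations of drug delivered transtympanically will be an order of magnitude less than the established safe serum levels" for the drugs' established uses. Section 1.1 gives the reference doses: 20-40 mg daily by mouth for istradefylline and, for regadenoson, "Recommended dosing is 0.4mg (within 5ml saline) intravenously".

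The preparations appear in sections 3.1 and 4.1. For istradefylline: "Istradefylline 1 mM stock solution will be prepared in 40-50% Dimethyl Sulfoxide (DMSO) and then diluted down to 200 nM". For regadenoson: "2.5 mg of drug dissolved in 2 ml DMSO before being diluted to 1:100 to give a 1% DMSO concentration". Both are then mixed with the poloxamer. For patients, section 5.2 says only: "Prepared drug-poloxamer gel solution will be placed in a 1ml syringe with a 22G spinal needle attached".

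Section 5.4 lists heart rate, oxygen saturation, blood pressure and ECG as routine monitoring during vestibular schwannoma surgery. Section 6 (Data Collection) lists intra-operative adverse events and serum drug levels but none of those monitored values. Section 5.4.1 has an independent committee review an intra-operative event that might be due to the drug, and allows for termination.

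**The concern.** The interim look is the only scheduled point at which the first patients' results are considered together before a second population is dosed. If it considers drug levels alone, it leaves out the component that bears most directly on harm: section 1.1 itself attributes regadenoson's systemic side effects to its cardiac action. A consistent shift in heart rate or blood pressure across six patients, which nobody classed as an adverse event, would enter neither the gate nor the section 5.4.1 review.

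The component that is kept would also carry little information if the amount of drug given is so small that levels must be low. A passed gate would then mainly confirm the preparation, yet could be read as evidence that systemic safety had been established.

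**Working it through.** The protocol gives no threshold, power or error rate for the interim, so there is no figure of its own to reproduce.

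**1. Gate against endpoint**

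| Section | Component named |
|---|---|
| 3.2, safety endpoint | plasma concentrations and cardiovascular effects |
| 3.1, condition for CI patients | systemic drug levels |

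This mismatch needs no assumption.

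**2. Largest possible amount of drug**

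Assumptions: the section 4.1 preparation is the one injected; the volume is at most 1 mL (syringe size, section 5.2); the gel dilutes it no further; all of it reaches the blood. The last two push the figure upwards.

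- Regadenoson: 2.5 mg / 2 mL / 100 = 0.0125 mg/mL, so at most 12.5 micrograms in 1 mL. Against 0.4 mg intravenously: 400 / 12.5 = 32, that is 1/32 or 3.1%. A 1:1 mix with gel would make it 1/64. Under linear kinetics, slow release of an amount cannot give a higher peak than the same amount given as a bolus, so 1/32 also bounds the peak level relative to that dose.
- Istradefylline: 200 nmol/L x 0.001 L = 0.2 nmol. The protocol gives no molar mass. At an assumed 300-500 g/mol this is 60-100 ng (0.06-0.10 micrograms). Against 20 mg: 20,000,000 ng / 100 ng = 200,000 and 20,000,000 / 60 = about 333,000. Against 40 mg: 400,000 to about 667,000. The reference is an oral dose; even if only 1% of it were absorbed, the smallest ratio would be 200,000 x 0.01 = 2,000.

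**3. What a plasma level could still show**

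If the 1:100 dilution of regadenoson were missed, 1 mL would hold 2.5 / 2 = 1.25 mg, and 1.25 / 0.4 = 3.1 times the intravenous dose. Levels therefore retain value as a check on preparation and delivery.

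**4. What six patients can say about events**

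This is a separate question from steps 1-3. With no event in n patients, the one-sided 95% upper limit for the event rate is 1 - 0.05^(1/n).

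- n = 6 (one drug at the interim): 1 - 0.05^(1/6) = 39.3%. The two-sided limit is 1 - 0.025^(1/6) = 45.9%.
- n = 10 (full recruitment for one drug): 1 - 0.05^(1/10) = 25.9%.

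The chance of seeing no event in six is (1 - p)^6: 53.1% at a true rate of 10% and 26.2% at 20%.

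**The case against.** The best defence is that the gate is not the only safeguard. Section 5.4.1 applies from the first patient: an event that might be due to the drug goes to an independent committee, dosing is reviewed, and the study can end. The anaesthetist watches for cardiac stress throughout. A reader might infer from the gate's wording that clinical events have no consequence, or that the gate cannot fail. The documents support neither. An attributable event among the first six can halt matters before the interim, and an unexpectedly high level could still block extension. What remains is that 5.4.1 reviews events singly and nothing ties its outcome to the decision on CI patients.

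Four further objections are fair:

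- The concentrations come from the in-vitro description, and section 5 does not say what patients receive. The mass balance is therefore conditional.
- The order-of-magnitude expectation in section 1 is background and concerns serum levels. It is not the gate's criterion. The absence of a numeric threshold is not held against the protocol either, since a statistical analysis plan may supply it.
- The sentence on extension speaks of safe levels, not of safety as such, and the statistical section calls the study exploratory. The 39% limit therefore does not contradict that sentence. It bears on the broader aim in section 3.1 of establishing systemic safety in these patients.
- Small numbers do not make the gate unable to fail. If events counted, at least one would be seen in six with probability 1 - 0.262 = 74% at a true rate of 20%.

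**Conclusion.** The inconsistency stands: section 3.1 opens the CI cohort on drug levels, while section 3.2 defines safety by levels and cardiovascular effects. This holds whatever is injected.

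That low levels are practically certain, and so say little about safety, holds on condition that the section 4.1 preparation is used at no more than 1 mL. The caps are then 1/32 of the intravenous dose for regadenoson and at most 1/200,000 of 20 mg for istradefylline, the latter at the assumed molar mass. The gate as worded is weakly informative rather than empty.

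Separately, an event-free interim for one drug would leave rates up to 39% unexcluded, so it should not be reported as having established systemic safety. The point is worth correcting before the first patient. It does not call the rest of the design into question, and it takes no position on which dose or volume is right.

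**What to change.** - **Section 3.1:** reconcile the condition for extension with section 3.2. For each drug, the interim decision should consider plasma levels together with the cardiovascular and adverse-event data of the six patients, including the outcome of any section 5.4.1 review. The investigators and the independent panel should set the safety limits.
- **Section 6 (Data Collection):** add the heart rate, blood pressure and ECG findings already monitored under section 5.4, so that the second component of the endpoint can be assessed.
- **Section 5.2:** state the concentration and volume given to patients, or refer to section 4.1 if that preparation applies, so that measured levels can be compared with the largest amount that could be present.
- **Reporting:** describe the interim as exploratory and, if no event occurs in six patients for a drug, give the 39% upper limit beside that result.

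The cost is revised wording, a few more recorded variables and a short review per drug. The monitoring is already routine, and no new standing committee or extra patients are needed.
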